10.1.9 Publication Policy

- The sponsor seeks to publish the results of these clinical trials in biomedical journals, whatever the outcome. Clinical trial results may also be presented at international congresses as posters or oral presentations.
- The results of this study may be published or presented at scientific meetings. If this is foreseen, the investigator should discuss specific publication concepts, including data to be covered, target congress/journal and proposed authors, with the sponsor for agreement before initiation. The investigator agrees to submit all manuscripts or abstracts to the sponsor before submission. This allows the sponsor to protect proprietary information and to provide comments.
- The sponsor will comply with the requirements for publication of study results. In accordance with standard editorial and ethical practice, the sponsor will generally support publication of multicentre studies only in their entirety and not as individual site data. In this case, a coordinating investigator will be designated by mutual agreement.
- Authorship will be determined by mutual agreement and in line with International Committee of Medical Journal Editors authorship requirements.

10.2 Appendix: Clinical Laboratory Tests

- Refer to SoA Section 1.3 for details of visits.
- The tests detailed in Table 5 will be performed by the local laboratory.
- Protocol-specific requirements for inclusion or exclusion of participants are detailed in Section 5 of the protocol.
- Additional tests may be performed at any time during the study as determined necessary by the investigator or required by local regulations.

Table 5 Protocol-Required Safety Laboratory Tests

Parameters	Screening	Intervention Period	EoS/ED
Haematology	X		X
Platelet Count	X		X
Haemoglobin	X		X
White blood cell count with differential:	X		X
Neutrophils			
Lymphocytes			
Monocytes			
Eosinophils			
Basophils			
Others			
Clinical Chemistry			
Creatinine	X		X
Glucose (non-fasting)	X		X
Aspartate Aminotransferase	X		X
Alanine Aminotransferase	X		X
Alkaline phosphatase	X		X
Bilirubin (total and conjugated)	X		X

EoS=end of study; ED=early discontinuation

Note: All parameters will be analysed locally. The preparation and storage of samples will be performed per each local laboratory practice.

Investigators must document their review of each laboratory safety report.

10.3 Appendix: AEs and SAEs: Definitions and Procedures for Recording, Evaluating, Follow-up, and Reporting**10.3.1 Definition of AE****AE Definition**

- An AE is any untoward medical occurrence in a clinical study participant, temporally associated with the use of study intervention, whether or not considered related to the study intervention.
- NOTE: An AE can therefore be any unfavourable and unintended sign (including an abnormal laboratory finding), symptom, or disease (new or exacerbated) temporally associated with the use of study intervention.

Events Meeting the AE Definition

- Any abnormal laboratory test results (haematology, clinical chemistry, or urinalysis) or other safety assessments (e.g. ECG, radiological scans, vital signs measurements), including those that worsen from baseline, considered clinically significant in the medical and scientific judgment of the investigator (i.e. not related to progression of underlying disease).
- Exacerbation of a chronic or intermittent pre-existing condition including either an increase in frequency and/or intensity of the condition.
- New condition detected or diagnosed after study intervention administration even though it may have been present before the start of the study.
- Signs, symptoms, or the clinical sequelae of a suspected intervention- intervention interaction.
- Signs, symptoms, or the clinical sequelae of a suspected overdose of either study intervention or a concomitant medication. Overdose per se will not be reported as an AE/SAE unless it is an intentional overdose taken with possible suicidal/self-harming intent. Such overdoses should be reported regardless of sequelae.
- “Lack of efficacy” or “failure of expected pharmacological action” per se will not be reported as an AE or SAE. Such instances will be captured in the efficacy assessments. However, the signs, symptoms, and/or clinical sequelae resulting from lack of efficacy will be reported as AE or SAE if they fulfil the definition of an AE or SAE.

Events NOT Meeting the AE Definition

- Any clinically significant abnormal laboratory findings or other abnormal safety assessments that are associated with the underlying disease, unless judged by the investigator to be more severe than expected for the participant’s condition.
- The disease/disorder being studied or expected progression, signs or symptoms of the disease/disorder being studied, unless more severe than expected for the participant’s condition.
- Medical or surgical procedure (e.g. endoscopy, appendectomy): the condition that leads to the procedure is the AE.

- Situations in which an untoward medical occurrence did not occur (social and/or convenience admission to a hospital).
- Anticipated day-to-day fluctuations of pre-existing disease(s) or condition(s) present or detected at the start of the study that do not worsen.

10.3.2 *Definition of SAE*

An SAE is defined as any untoward medical occurrence that, at any dose, meets one or more of the criteria listed:

a. Results in death

b. Is life-threatening

The term 'life-threatening' in the definition of 'serious' refers to an event in which the participant was at risk of death at the time of the event. It does not refer to an event, which hypothetically might have caused death, if it were more severe.

c. Requires inpatient hospitalisation or prolongation of existing hospitalisation

In general, hospitalisation signifies that the participant has been admitted (usually involving at least an overnight stay) at the hospital or emergency ward for observation and/or treatment that would not have been appropriate in the physician's office or outpatient setting. Complications that occur during hospitalisation are AEs. If a complication prolongs hospitalization or fulfils any other serious criteria, the event is serious. When in doubt as to whether 'hospitalisation' occurred or was necessary, the AE should be considered serious.

Hospitalisation for elective treatment of a pre-existing condition that did not worsen from baseline is not considered an AE.

d. Results in persistent or significant disability/incapacity

The term disability means a substantial disruption of a person's ability to conduct normal life functions.

This definition is not intended to include experiences of relatively minor medical significance such as uncomplicated headache, nausea, vomiting, diarrhoea, influenza and accidental trauma (e.g. sprained ankle) that may interfere with or prevent everyday life functions but do not constitute a substantial disruption.

e. Is a congenital abnormality /birth defect

f. Other situations:

Medical or scientific judgment should be exercised by the investigator in deciding whether SAE reporting is appropriate in other situations such as significant medical events that may jeopardize the participant or may require medical or surgical intervention to prevent one of the other outcomes listed in the above definition. These events should usually be considered serious.

Examples of such events include invasive or malignant cancers, intensive treatment for allergic bronchospasm, blood dyscrasias, convulsions or development of intervention dependency or intervention abuse.

10.3.3 Recording and Follow-Up of AE and/or SAE

AE and SAE Recording

- When an AE/SAE occurs, it is the responsibility of the investigator to review all documentation (e.g. hospital progress notes, laboratory reports, and diagnostics reports) related to the event.
- The investigator will then record all relevant AE/SAE information.
- It is **not** acceptable for the investigator to send photocopies of the participant's medical records to the sponsor in lieu of completion of the required forms.
- There may be instances when copies of medical records for certain cases are requested by the sponsor. In this case, all participant identifiers, with the exception of the participant number, will be redacted on the copies of the medical records before submission to the sponsor.
- The investigator will attempt to establish a diagnosis of the event based on signs, symptoms, and/or other clinical information. Whenever possible, the diagnosis (not the individual signs/symptoms) will be documented as the AE/SAE.

Assessment of Intensity

- The investigator will make an assessment of intensity for each AE and SAE reported during the study using the National Cancer Institute - Common Toxicity Criteria for AEs (NCI-CTCAE) (version 5.0 or higher).

Where:

- Grade 1:** Mild; symptoms do not alter the participant's normal functioning.
- Grade 2:** Moderate; symptoms produce some degree of impairment to function, but are not hazardous, uncomfortable or embarrassing to the participant.
- Grade 3:** Severe; symptoms definitely hazardous to wellbeing or causing significant impairment of function or incapacitation.
- Grade 4:** Life-threatening; any event that places the participant at immediate risk of death from the event as it occurred, i.e. it does not include a reaction that, had it occurred in a more severe form, might have caused death.
- Grade 5:** Death related to AE

An event is defined as "serious" when it meets at least one of the predefined outcomes as described in the definition of an SAE, NOT when it is rated as severe.

Assessment of Causality

- The investigator is obligated to assess the relationship between study intervention and each occurrence of each AE/SAE. The investigator will use clinical judgment to determine the relationship.
- A "reasonable possibility" of a relationship conveys that there are facts, evidence, and/or arguments to suggest a causal relationship, rather than a relationship cannot be ruled out.
- Alternative causes, such as underlying disease(s), concomitant therapy, and other risk factors, as well as the temporal relationship of the event to study intervention administration will be considered and investigated.

- The investigator will also consult the Investigator's Brochure (IB) and/or Product Information, for marketed products, in his/her assessment.
- For each AE/SAE, the investigator **must** document in the medical notes that he/she has reviewed the AE/SAE and has provided an assessment of causality.
- There may be situations in which an SAE has occurred, and the investigator has minimal information to include in the initial report to the sponsor. However, it is very important that the investigator always make an assessment of causality for every event before the initial transmission of the SAE data to the sponsor.
- The investigator may change his/her opinion of causality in light of follow-up information and send an SAE follow-up report with the updated causality assessment.
- The causality assessment is one of the criteria used when determining regulatory reporting requirements.

Follow-up of AEs and SAEs

- The investigator is obligated to perform or arrange for the conduct of supplemental measurements and/or evaluations as medically indicated or as requested by the sponsor to elucidate the nature and/or causality of the AE or SAE as fully as possible. This may include additional laboratory tests or investigations, histopathological examinations, or consultation with other health care professionals.
- If a participant dies during participation in the study or during a recognised follow-up period, the investigator will provide the sponsor with a copy of any post-mortem findings including histopathology.
- New or updated information will be recorded in the eCRF.
- The investigator or qualified designee will submit any updated SAE data to the sponsor within 24 hours of receipt of the information.

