Subcutaneous injection of triptorelin 11.25 mg (3-month formulation) has been evaluated in an open-label, single-arm study where treatment was administered twice over a 6-month period [Lebret 2015]. Results showed subcutaneous injection of triptorelin was well tolerated and maintained castration for up to 6 months, similarly, to results from studies with triptorelin administered intramuscularly. Furthermore, results from a clinical study with triptorelin enbionate 22.5 mg (6-month formulation) administered twice subcutaneously over a 1-year period in participants with advanced prostate cancer who were non-castrated, showed induction and maintenance of castration (i.e. serum testosterone <1.735 nmol/L) in the majority of participants (82.6%) (data on file). Subcutaneous injection of triptorelin 22.5 mg was also well tolerated, with mild to moderate injection site AEs reported in 5.0% of participants.

A more detailed description of the product, including further details on administration procedures and dosage are provided in Section 6.

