2.3.1 Risk Assessment

A risk assessment for this study is provided in Table 2.

Table 2 Study Risk Assessment

Potential Risk of Clinical Significance	Summary of Data/Rationale for Risk	Mitigation Strategy
Study Intervention: Triptorelin		

There is no major known nonclinical risk associated with the study intervention
 
Clinical risks associated with the study intervention may include:
 
 • hot flushes • erectile dysfunction • loss of libido • impaired physical activities • metabolic syndrome • cardiovascular events • anxiety/depression • decreased bone mineral density • risk of abortion or foetal abnormality [a] 
For a full list of adverse events and safety concerns with the product, please refer to the locally approved SmPC
	
See approved SmPC
	
Participant selection: Participants with significant medical conditions will be excluded from the study (see Section 5.1 and 5.2).
 
Participant monitoring: During the study, there will be close monitoring of the participants for safety including local tolerability (see Section 8.3.6)
 
Withdrawal criteria: Participants who become at risk due to any AE or medical condition will be withdrawn from the study intervention.

Study Procedures		
There are no specific risks related to the study design or procedures.	All procedures requested for the study are commonly used in clinical practice and the design does not create any specific risk or delay possible therapeutic option for participants	Not applicable

Abbreviations: SmPC=Summary of Product Characteristics

a Pregnancy is highly unlikely in this study population. However, reproductive risks are listed for completeness for female partners of participants who may become pregnant.

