5.8 Safety

5.8.1 General Consideration

All safety summaries and analyses will be based upon the Safety Set. All safety data will be included in subject data listings (see listing detail conventions in [Appendix 4](#)).

Associated Procedure / Instruction Reference	319480-SOP
Form Reference	080091-FOR v7.0

Baseline value definition is given in section [5.1.3](#).

5.8.2 *Extent of Exposure*

Administration of triptorelin embonate 22.5 mg 6-month formulation will be summarized by descriptive statistics for the following: duration of exposure, number of injections administered, number of subjects with at least one dose reduction or injection delayed. Duration of exposure will be defined in months as:

$([\text{last dose date} - \text{first dose date}] + 1) / (365.25/12)$.

- Exposure listing will also be generated.

5.8.3 *Adverse Event*

All adverse events (AEs) recorded in the eCRF will be coded using MedDRA dictionary. All AEs will be classified by MedDRA PT and SOC. Severity will be graded according to the National Cancer Institute - Common Terminology Criteria for Adverse Events (NCI-CTCAE) Version 5.0 or higher. Adverse events will be classified as TEAEs if meeting one of the rules below:

- Events with start date/time on or after the date/time of first IMP administration and within 168 days after the last dose of study treatment, or up to Day 337, whichever is later.
- Events whose severity worsens on or after the date/time of first IMP administration,

For AE with partial or missing start date, refer to [Appendix 2](#) for TEAE determination algorithm.

In the case where it is not possible to define an AE as treatment emergent or not, the AE will be classified by the most conservative case; i.e. treatment emergent.

The following summaries will be presented:

- Overview of TEAE,
- TEAE by SOC and PT,
- TEAE by PT,
- Most common ($\geq 10\%$) TEAEs by SOC and PT,
- TEAE by SOC, PT, and worst toxicity grade,
- Grade 3 or 4 TEAE by SOC and PT,
- TEAE by SOC, PT, and treatment relationship,
- Treatment-related TEAE by SOC, PT, and worst toxicity grade,
- Grade 3 or 4 treatment-related TEAE by SOC and PT,
- Non-serious TEAE by SOC and PT.

TEAE summaries will be presented in decreasing frequency of SOC, decreasing frequency of PT within SOC, and then in alphabetical order. TEAE summaries by PT will be presented in decreasing frequency of PT, and then alphabetically.

Multiple occurrence of TEAEs will be presented as follows:

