- Participants will be counted at most once at the PT, and at most once at the SOC;

Associated Procedure / Instruction Reference	319480-SOP
Form Reference	080091-FOR v7.0

IPSEN GROUP

CONFIDENTIAL

D-FR-52014-245

SAP Final: Version 1.0: 30 January 2023

PAGE 22/43

- Participants reporting multiple TEAEs coded within the same SOC/ PT will be presented in the worst-case grade category (grade order: 5>4>3>2>1>missing) ever reported in that SOC/PT;
- Participants reporting multiple TEAEs coded within the same SOC/ PT will be presented in the TEAE with the worst-case relationship to study treatment (order: related > not related > missing) ever reported;
- For TEAE summary by worst toxicity grade, participants reported single occurrence TEAE while the associated toxicity grade is missing, the participant will be presented in the toxicity grade missing category;
- TEAEs with missing relationship to study treatment will be considered treatment-related in the summary.

The number of events will also be displayed in the summary tables, when applicable.

Deaths, SAEs, and Other Significant Adverse Events

The following summaries will be presented:

- Serious TEAE by SOC and PT,
- Most common ($\geq 5\%$) serious TEAEs by SOC and PT,
- Treatment-related serious TEAE by SOC and PT,
- TEAEs leading to treatment discontinuation by SOC and PT,
- TEAE leading to treatment interruption by SOC and PT,
- TEAEs leading to a dose reduction by SOC and PT,
- Death summary.

By-subject listing will be produced for all AEs, all serious adverse events (SAEs), all AEs leading to dose reduction, treatment interruption, treatment discontinuation, and fatal AE. Treatment emergence status will be flagged in the listing whenever applicable.

5.8.4 *Laboratory Data*

Clinical safety laboratory tests will be assessed by local laboratories. All laboratory data will be presented in the units of International System of Units (SI).

Haematological and biochemical toxicities will be graded according to the NCI-CTCAE criteria, where available. The toxicity grades will be assigned programmatically by applying the NCI-CTCAE guideline as described in Section 7 (11). All scheduled and unscheduled laboratory test results will be included in the worst toxicity grade summary. For white blood cells, neutrophils, platelets and haemoglobin, with associated grade 3 or 4 toxicities, nadir and day to nadir from most recent injection will be presented in the listing.

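### The printed Grade 2 anchor in Protocol 10.3.3 shuts out uncomfortable or embarrassing symptoms, so it leaves a gap below Grade 3 and can conflict with the NCI-CTCAE instruction it follows

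*Protocol*

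**What the plan says.** Protocol 10.3.3, under Assessment of Intensity, opens with the governing instruction: "The investigator will make an assessment of intensity for each AE and SAE reported during the study using the National Cancer Institute" and the rest of the NCI-CTCAE name, version 5.0 or higher. One-line anchors for Grades 1 to 5 follow directly, introduced as explaining that scale.

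- Grade 1 (mild): the participant's normal functioning is unaffected. Discomfort is not mentioned.
- The moderate level, Grade 2, is worded as follows: "symptoms produce some degree of impairment to function, but are not hazardous, uncomfortable or embarrassing to the participant".
- For the severe level, Grade 3, the wording is: "symptoms definitely hazardous to wellbeing or causing significant impairment of function or incapacitation".
- Grades 4 and 5: immediate risk of death, and death.

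The protocol synopsis, Protocol 9.4.3 and SAP 5.8.3 also name CTCAE version 5.0 or higher. None of them repeats the anchors, and no passage says which source prevails if the two disagree.

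The grades feed four SAP 5.8.3 summaries: TEAEs by worst grade, "Grade 3 or 4 TEAE by SOC and PT", and the treatment-related version of each. Where a participant has several TEAEs in one SOC or PT, the worst is taken with "grade order: 5>4>3>2>1>missing". A single TEAE without a grade goes into a separate missing category.

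**The concern.** The events that the Grade 2 anchor handles badly are among those expected in this trial. The risk table in Protocol 2.3.1 lists hot flushes, "erectile dysfunction" and loss of libido. The local tolerance check in Protocol 8.3.6 includes tenderness, pain and itching. Discomfort or embarrassment is an ordinary feature of such events.

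The anchors are the only grade definitions printed in the protocol, so a site may well work from them. SAP 5.7.1.3 lists seven countries. If some sites use the anchors and others use CTCAE, both comply with 10.3.3, yet the severity tables would mix two scales. For non-laboratory events the SAP plans no regrading that would put this right.

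TEAE status can also be touched. Under Protocol 9.4.3 and SAP 5.8.3, an event present before the first dose becomes treatment-emergent only if its intensity increases. Inclusion criterion 3 requires at least 3 months of GnRH analogue before screening, so hot flushes or erectile dysfunction may already be present on Day 1. Whether a worsening is recorded may then depend on whether a site believes it can assign Grade 2. TEAE incidence is a secondary endpoint.

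**Working it through.** No calculation applies. The question is whether the printed anchors cover every kind of non-fatal event without immediate risk of death. Three features appear in the wording of Grades 1 to 3: impairment of function (none, some, significant), hazard (no, definite) and discomfort or embarrassment (no, yes). That gives 3 × 2 × 2 = 12 combinations. Reading the negative in Grade 2 as governing all three adjectives:

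| Impairment | Hazard | Uncomfortable or embarrassing | Printed anchor met |
|---|---|---|---|
| None | No | No or yes | Grade 1 |
| None | Definite | No or yes | Grade 3 |
| Some | No | No | Grade 2 |
| Some | No | Yes | None |
| Some | Definite | No or yes | Grade 3 |
| Significant | Either | No or yes | Grade 3 |

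The rows account for 2 + 2 + 1 + 1 + 2 + 4 = 12 combinations, and one is uncovered. It fails Grade 1 because function is altered, Grade 2 because the symptom is uncomfortable or embarrassing, and Grade 3 because it is neither definitely hazardous nor significantly impairing.

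The printed scale is also out of order on this feature. An uncomfortable symptom can be Grade 1, which is silent on discomfort, but never Grade 2.

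Next, does anything later in the plan repair a grade assigned this way? SAP 5.8.4 says of laboratory toxicities: "The toxicity grades will be assigned programmatically by applying the NCI-CTCAE guideline". SAP section 7, item 11, is likewise limited to laboratory parameters. For all other events the recorded grade goes into the tables unchanged.

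Finally, can the effect be sized? That would need the number of events in the uncovered combination and the share of sites using the anchors rather than CTCAE. The documents give neither. They also do not reproduce the CTCAE criteria by term, so the grade that CTCAE would give a particular event cannot be set against the anchor here.

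**The case against.** The strongest reply is that CTCAE governs. It is the instrument named in the instruction itself and in three other places, so an investigator who follows it always has a scale to use. This stands. The gap belongs to the anchors, and it would be wrong to say that such an event has no grade under the protocol as a whole. It does not remove the problem, because the anchors are presented as the meaning of the scale and no precedence rule is given.

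A second reply is that most investigators would choose Grade 2 anyway, since that line is labelled moderate and speaks of some impairment. The negative may have been meant for the hazard alone. Both are plausible. A reader might infer that sites are forced to grade up, grade down or leave the grade blank, but that omits this natural choice. The anchors give no particular reason to grade up, because the event fails Grade 3 as well. A probable drafting slip is still a reason to correct the text.

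A third reply is that TEAE incidence does not depend on grade. That is right for events that first appear after dosing. It is only partly right overall, because of the worsening rule for pre-existing events.

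**Conclusion.** The point holds as a wording defect with a risk of inconsistent grading. Read literally, the printed anchors leave one kind of event uncovered, and that kind can include listed risks and local reactions in this trial. The outputs at risk are the worst-grade and Grade 3 or 4 TEAE tables and the recording of worsening in pre-existing events. Size and direction are unknown. The conclusion rests on the literal reading of Grade 2 and on at least some sites using the anchors. The testosterone-based primary endpoint is unaffected. So is seriousness, which 10.3.3 separates from severity.

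Three stronger readings are tempting, and the documents do not support them:

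- That the severity tables are distorted, or the Grade 3 or 4 rate inflated. The documents give no rate of affected events and no direction of shift.
- That laboratory adverse events are graded by symptoms in one table and by values in another. The synopsis applies CTCAE to laboratory abnormalities, and Protocol 9.4.3 requires haematological and biochemical toxicities to be graded by CTCAE where available.
- That a comparison with the earlier subcutaneous study is spoiled. Protocol 2.2 reports "mild to moderate injection site AEs reported in 5.0% of participants", which pools the two categories, so a shift between Grades 1 and 2 would not change it. This study is non-comparative and plans no such comparison.

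**What to change.** In Protocol 10.3.3, delete the Grade 1 to 5 anchors and require each adverse event to be graded by the CTCAE version 5.0 criteria for its term.

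If generic anchors are wanted for terms that CTCAE does not cover, keep them for that purpose only and state that CTCAE prevails wherever it has criteria. Reword Grade 2 so that discomfort or embarrassment does not exclude it, for example: *some impairment of function; may be uncomfortable or embarrassing; not hazardous*.

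The cost is protocol wording, a short note to sites and possibly queries on adverse events already graded under the present anchors. The SAP tables and their programming need no change.
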